Lidocaine is a globally available and inexpensive medication traditionally used for anesthesia of specific body parts. Intravenous infusion of lidocaine has been proven to be an economical and convenient method that can alleviate widespread inflammatory reactions during surgery [4], and animal experiments have shown that it can also inhibit the proliferation of lung cancer [5]. In vitro studies have shown that lidocaine can inhibit cancer cell proliferation and induce cancer cell death by reducing the epidermal growth factor receptor (EGFR) response and inhibiting the activation of matrix metalloproteinase-9, which is crucial for extracellular matrix degradation in malignant cells. Lidocaine can also regulate gene expression by altering the DNA of malignant cells, thereby reducing cancer growth and metastasis [6]. In addition, studies have shown that the sympathetic nervous system has an impact on the survival microenvironment of lung cancer, which can weaken the effectiveness of postoperative chemotherapy [7]. However, lidocaine can inhibit the excitation of the sympathetic nervous system, indicating the potential value of lidocaine.

Surgical stress response leads to the release of pro-inflammatory cytokines and inhibition of immune cell function [3]. Lidocaine has been shown to alleviate inflammation in an in vivo model by reducing cytokine

release and subsequent metastasis. The clinical therapeutic dose of lidocaine can also enhance the function of NK cells [8]. There are a large number of NK cells in the lungs of lung cancer patients, which play a key role in eliminating lung cancer and preventing metastasis formation [9]. In addition, lidocaine can block Src activation, thereby reducing the invasiveness of cancer cells [10].

The consequences of cancer recurrence and metastasis highlight the necessity of intervention in terms of increasing incidence rate, mortality and financial burden [11]. A Cochrane review emphasized the necessity of well-designed randomized controlled trials to reduce cancer recurrence.

Cancer staging is indeed associated with recurrence, especially when cancer cells migrate from the primary site. Stage I ground glass nodules, even if the pathological type is invasive adenocarcinoma and larger than 3cm, still have a 5-year 100% survival rate. Stage III and IV lung cancer, due to the invasive spread of cancer, surgery is usually not for cure, but mainly for symptom relief, and lidocaine is unlikely to provide benefits. Stage I solid nodular lung cancer involves vascular and pleural invasion, while stage II involves vascular and lymphatic system invasion, requiring extensive surgical resection [12]. These patients may benefit the most from lidocaine and will be the main target of this study. We will recruit patients with all cancer stages to understand potential differences in

response to lidocaine treatment.

Lidocaine has an inhibitory effect on tumor cells, which is mostly based on animal studies, and toxic doses are often used in animal studies. There are few high-quality studies in clinical practice. This study aims to explore whether lidocaine infusion at a safe dose can bring the value of prolonging survival for lung cancer patients after surgery, which is of great significance.

Research objective

1. Main objective: To evaluate the effect of perioperative lidocaine infusion on postoperative reoccurrence and metastasis in patients with non-small cell lung cancer.
2. Secondary objective: To explore the value of perioperative lidocaine infusion in prolonging the survival of patients with non-small cell lung cancer

Research design types, principles, and experimental procedures

1. Research Design

This is a 1:1 parallel double-blind (patient and data collector blinded, prepared by anesthesia nurses and administered by anesthesiologists) randomized controlled trial comparing the efficacy of intravenous infusion of lidocaine versus placebo/saline during minimally invasive (thoracoscopic or robotic) surgery in lung cancer patients.

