5. Postoperative analgesia management

To reduce the possibility of confounding factors, general

anesthesia should be maintained under a combination of intravenous and inhalation anesthesia. Postoperative care follows the unit's standard to enhance postoperative rehabilitation protocol. The pain control program will be consistent with the unit's standard procedure. However, during IMP infusion, simultaneous continuous infusion of other local anesthetic drugs (such as epidural or wound catheters) cannot be performed. After the surgery, all patients were uniformly treated with sufentanil 2ug/kg diluted to 100ml and pumped with 2ml/h for intravenous analgesia

6. Randomization

After obtaining consent, participants will be randomly assigned (1:1) to receive intravenous lidocaine or placebo using a minimization algorithm. The minimum criteria include age (<45 years, 45-65 years, 65-80 years), gender, trial center.

6. Observation project

Main outcome measure

Assess the reoccurrence time of lung cancer patients within 36 months from the date of surgery.

Secondary outcome measure

1. Disease free survival (DFS)
2. Objective remission rate of patients' diseases
3. Health related Quality of Life Questionnaire EQ-5D-5L
4. Cancer specific quality of life measured using the Functional

Assessment of Cancer Therapy (FACT-L) questionnaire.

Other observation indicators

1. The total length of hospital stay, including readmission, is 36 months.
2. Changes in pro-inflammatory cytokine levels (IL-6, TNG - α) from baseline on the third day after treatment and upon discharge.

On the 1st and 3rd day after treatment and at discharge, changes in reticular fiber dissolution markers (matrix metalloproteinases MMP-9, MMP-2) from baseline were observed.

3. Perioperative nausea, vomiting, delirium, pain control, and incidence of cardiovascular accidents 6 and 12 months after treatment completion.

7. Efficacy evaluation criteria

Follow up chest CT scans at 6, 12, 18, 24, and 36 months after surgery were conducted to evaluate whether lung cancer patients had cancer reoccurrence and the time of reoccurrence within 36 months from the date of surgery. And evaluate the cancer specific quality of life using the lung cancer treatment function assessment questionnaire for patients. The shortened recurrence time and improved specific quality of life indicate therapeutic efficacy.

8. Observation of adverse events

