Statistics will be recorded and managed using Redcap data, and analyzed using SPSS21 software. The analysis will be conducted according to the intention to treat principle. The statistical analysis plan for this study includes summarizing baseline data, conducting primary outcome analysis using time to event analysis, and conducting additional survival analysis. Baseline variables such as age group, gender, comorbidities, ASA classification, cancer stage, cancer TNM classification, pathological type, neoadjuvant targeted therapy, radiotherapy, and chemotherapy will be summarized using appropriate descriptive statistical methods, using mean and standard deviation or median and quartile range (depending on the applicability of continuous variables). The categorical variables will be summarized using the frequency and percentage of participants in each category. Researchers will use EDC to fill out CRF. The data will be stored on a secure server.

The source documents of CRF report information will be archived in the center and available for monitoring, IRB/IEC review, and regulatory inspection as needed. According to applicable regulations, researchers must retain all research records/documents.

The main outcome is defined as the time of cancer reoccurrence within 36 months after surgery in patients with stage I and II lung cancer. Multiple Cox regression models will be used to analyze the main results and adjust the truncated data. The truncated data includes participants who have not experienced recurrence or death within 36 months, as well as those who have been lost to follow-up or withdrawn from the study.

The risk ratio will be estimated by comparing the risk rates of the placebo group and the lidocaine group, taking into account the truncated data of the participants and adjusting for covariates. In addition, Kaplan Meier plots will be used to visualize and compare survival distributions, while Log rank tests will evaluate the differences between the two groups.

We will use the study drug allocation ($x=0$ placebo, $x=1$ lidocaine) as the independent variable, the time of cancer recurrence or death as the dependent variable, and age group (<45, 45-65, 65-80), gender, number of comorbidities, ASA classification, cancer staging, neoadjuvant radiotherapy, and chemotherapy as adjusted covariates.

Clean the experimental data and construct an analysis dataset suitable for statistical analysis. Data quality control is achieved through the accuracy

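### The survival objective has no death endpoint: overall survival is not listed, and the undefined DFS, in its usual sense, repeats the event already used in the primary Cox model

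*Protocol*

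**What the plan says.** Under Research objective, the protocol separates two aims. The main one concerns recurrence and metastasis after surgery. The secondary one is "To explore the value of perioperative lidocaine infusion in prolonging the survival of patients with non-small cell lung cancer". The background just before it describes the whole study as asking whether a safe dose "can bring the value of prolonging survival for lung cancer patients after surgery".

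Under section 6, Observation project, the main outcome is to "Assess the reoccurrence time of lung cancer patients within 36 months from the date of surgery". The four secondary outcomes are DFS (no definition, time origin or horizon given), "Objective remission rate of patients' diseases", the EQ-5D-5L and the FACT-L. The other indicators are hospital stay, cytokines, matrix metalloproteinases and perioperative or cardiovascular events.

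Under section 10, Statistics process, the outcome is again recurrence only: "The main outcome is defined as the time of cancer reoccurrence within 36 months after surgery". The same section then has the Cox model take "the time of cancer recurrence or death as the dependent variable". Its censored group consists of "participants who have not experienced recurrence or death within 36 months" together with those lost to follow-up or withdrawn. It also mentions an additional survival analysis without naming its endpoint.

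**The concern.** Recurrence is already the main objective, so the natural reading of a separate survival objective is length of life. No listed outcome measures that. The one survival-type outcome, DFS, appears to share its event with the primary model. A survival statement at the end of the trial would then rest either on the primary result reported under a second name or on an analysis whose endpoint the protocol does not name.

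There is also a data risk. A first-event model needs nothing after recurrence. If overall survival is not an outcome, nothing in the protocol requires vital status to be followed in patients whose disease has recurred, and their deaths matter for a survival question.

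**Working it through.** No figure in the protocol bears on this point. The check sets the objectives, the outcome list and the model side by side.

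**Step 1: is there an outcome for death?** Of the four secondary outcomes, one (DFS) is of survival type and none is death from any cause. None of the other indicators is death either.

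**Step 2: what is the event in the primary analysis?** The two outcome statements say recurrence. The dependent variable in section 10 says recurrence or death. The censoring rule agrees with the model: a patient who dies without recurrence is not in the group free of both events at 36 months, nor among those lost or withdrawn, so that patient has to be counted as an event. Two sentences in section 10 thus treat death as an event, and two statements of the outcome do not.

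**Step 3: how does each endpoint treat each patient?** DFS is taken in its usual sense, with the same time origin and 36-month horizon as the primary. Both are assumptions, because the protocol gives no definition.

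| Course to 36 months | Primary as stated (recurrence) | Primary as modelled (recurrence or death) | DFS, usual sense | Overall survival (not listed) |
|---|---|---|---|---|
| Recurs, then dies | Event at recurrence | Event at recurrence | Event at recurrence | Event at death |
| Recurs, alive | Event at recurrence | Event at recurrence | Event at recurrence | Censored |
| Dies without recurrence | Not an event; handling not stated | Event at death | Event at death | Event at death |
| Neither | Censored | Censored | Censored | Censored |

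The third and fourth columns agree in every row. Under these assumptions and with the same covariates, the DFS analysis is the primary analysis. The second column differs from DFS only in patients who die without recurrence. Overall survival differs from all three in every patient who recurs.

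**Step 4: are the data for overall survival already collected?** Only in part. The primary model needs deaths that come before recurrence. Section 7 (Efficacy evaluation criteria) schedules chest CT at 6, 12, 18, 24 and 36 months to find recurrence and its time, and no section sets survival follow-up after recurrence. The termination criteria include worsening of the condition, which could be read as ending observation at that point. Section 9 promises outcome data on all randomised participants, but overall survival is not among the outcomes.

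**Step 5: what could overall survival show?** The protocol gives no survival rate or survival effect, so no power can be computed. Under Research time, work runs from January 2026 and data collection ends in October 2028, about 34 months. If those dates describe enrolment, the first patients have at most about 34 months of follow-up at analysis, and the last 400 (January to October 2028) at most about 10.

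**The case against.** The best case for the plan has four parts.

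- **DFS is a survival measure.** The objective says survival without specifying overall survival, and DFS is the first secondary outcome. A reader might infer that the objective cannot be answered at all; the documents do not support that. But if DFS is the intended measure, the two objectives share one analysis as the model is now written.
- **The overlap is conditional.** A reader might infer that the DFS and primary hazard ratios must be equal. That needs a DFS definition and horizon that the protocol does not give, and it lets the model sentence override an outcome stated twice as recurrence only. Under that stated outcome, DFS is a distinct endpoint. This stands, but then the model and censoring rule are wrong for the primary outcome, so a correction is needed on either reading.
- **Details may be left to the SAP.** This is fair for the covariates, the method and the exact DFS rules. The choice of endpoint for a stated objective, and the follow-up it needs, belong in the protocol. An additional survival analysis with no named event does not supply them.
- **Overall survival will be immature.** The timetable supports this, and the background itself cites 100% five-year survival for stage I ground-glass nodules, which the inclusion criteria do not exclude. It argues for a descriptive role, which fits an objective that is only exploratory.

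**Conclusion.** The point holds as a mismatch between objective and endpoints. One of two stated objectives has no dedicated outcome, and as modelled it would be answered only by repeating the primary result. Behind this lies a conflict within the protocol: recurrence alone as the stated primary outcome, recurrence or death as the modelled event.

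The absence of a death outcome and the conflict over the primary event are read directly from the text. The duplication rests on the usual meaning of DFS, a common 36-month horizon, and the model sentence being followed as written.

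A reader might also infer that overall survival could be added with no new data, because death is already in the model. That is not so: deaths after recurrence never enter a first-event analysis.

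The primary comparison remains feasible, so this is a change that should be made rather than a fatal flaw.

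**What to change.** 1. **Section 6, Secondary outcome measure.** List overall survival as an exploratory outcome: time from surgery or randomisation (state which) to death from any cause, censored at the date last known alive, analysed with the same Cox model as the primary. State that vital status is followed after recurrence to the end of follow-up.
2. **Section 10, Statistics process.** Make the primary event recurrence, as the outcome is stated, with death before recurrence handled as a competing event, and correct the censoring rule to match.
3. **DFS.** Define it as recurrence or death, with its origin and horizon, so that it is distinct from the primary.
4. **Alternative to 2 and 3.** If the sponsor prefers recurrence or death as the primary, call it DFS throughout and drop the duplicate secondary outcome. Item 1 is still needed for the survival objective.

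**Cost.** Items 2 to 4 are wording. Item 1 adds one real requirement, vital-status follow-up after recurrence, which is easiest to set up before the planned start in January 2026. The total of 1400 patients was derived from recurrence times (medians of 18 and 24 months, 18/24 = 0.75), so adding an exploratory outcome does not change it. Under item 2, deaths without recurrence no longer count as primary events; the protocol gives no figure for how many that would be. Few deaths are likely on the stated timetable, so overall survival should be reported descriptively.

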1.1 Sample size calculation

For the time to event outcome, use the median reoccurrence time of similar populations in the literature to estimate the hazard ratio (HR). The median reoccurrence time described in the literature is 18 months. If we do not want to miss the 6-month improvement in event time in the treatment group, then HR estimates the risk ratio of reoccurrence time at 18 months in the control group and 24 months in the treatment group.

Risk ratio=(risk rate of treatment group)/(risk rate of control group)

Risk rate=1/(median recurrence time)

Therefore, the risk ratio can be estimated as: Risk ratio=(1/24)/(1/18)=18/24=0.75

The estimated risk ratio is 0.75, which represents a 25% reduction in risk effect for the treatment group compared to the control group. The sample size is based on the parallel design of the superiority program, survival endpoint, 90% efficacy, 0.05 significance level, bilateral significance level, HR 0.75. Using PASS11 software, it is estimated that each group requires 635 cases, and an increase of 10% would result in 700 cases per group. Therefore, the planned total sample size is 1400 patients with lung cancer.

2、 Case selection

In this experiment, qualified participants will be recruited from each center, as the annual number of lung surgeries in each center reaches around 8000 cases.

Inclusion Criteria

1. Age range: 18-80 years old.
2. Electively undergo minimally invasive (thoracoscopic or robotic) surgery for clinical stage I and II lung cancer.
3. Willing and capable of providing consent.

Exclusion criteria

1. Palliative surgery without intention of cure.

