(numerical range), reasonableness (whether the category is reasonable), and handling of missing data (by checking and supplementing missing data). Then conduct statistical analysis. Missing data will be compensated through multiple imputation and pattern mixing methods to explore the robustness of treatment effect estimation. We will explore the reasons for missing data, such as loss to follow-up or withdrawal, and report them. We will seek clarification of missing data through routine data collection with the clinical team. Resolve data queries before analysis.

11、 Ethics in Clinical Research

Clinical research will follow relevant regulations such as the Helsinki Declaration of the World Medical Assembly. The clinical study will only be conducted after the ethics committee approves the trial protocol before the start of the research. Before each participant is enrolled in this study, the researcher is responsible for fully and comprehensively introducing the purpose, procedures, and potential risks of this study to the participant or their representative, and signing a written informed consent form. The participant should be informed of their right to withdraw from this study at any time, and the informed consent form should be kept as a clinical research document for future reference. During the research process, the personal privacy and data confidentiality of the subjects will be protected.

Research time

January 2026 December 2026: Project initiation, completion of data

collection for 400 patients

January 2027 December 2027: Complete data collection and mid-term analysis for 600 patients

January 2028 to October 2028: Complete data collection for 400 patients

October 2028 to December 2028: Data organization and statistical analysis. Complete the paper writing and submit the SCI paper as soon as possible.

Reference

1. 蔡林, 朱称心, 张兴龙, 房怡, 杨海燕, 郭兰伟: 全球肺癌流行数据解读. 中华流行病学杂志 2024, 45(04):585-590.
3. Ben-Eliyahu S, Golan T: Harnessing the Perioperative Period to Improve Long-term Cancer Outcomes. JNCI: Journal of the National Cancer Institute 2018, 110(10):1137-1138.
4. Wall TP, Buggy DJ: Perioperative Intravenous Lidocaine and Metastatic Cancer Recurrence - A Narrative Review. Frontiers in Oncology 2021, 11.

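### The 635 per group and 90% power do not follow from the stated 18- and 24-month medians over the 36-month outcome window; those inputs need about 364 to 369 per group

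*Protocol*

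**What the plan says.** Section 1.1 (Sample size calculation) takes a median time to recurrence of 18 months from the literature and a 6-month improvement as the effect not to be missed: "HR estimates the risk ratio of reoccurrence time at 18 months in the control group and 24 months in the treatment group". It sets the hazard equal to the reciprocal of the median, obtains a hazard ratio of 18/24 = 0.75, and adds 90% power and a two-sided 0.05 level. The result is "Using PASS11 software, it is estimated that each group requires 635 cases, and an increase of 10% would result in 700 cases per group", hence 1400 in total. The section gives no required number of events, event proportion, accrual period or follow-up time.

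The follow-up is fixed elsewhere. Under Main outcome measure: "Assess the reoccurrence time of lung cancer patients within 36 months from the date of surgery". Section 10 (Statistics process) repeats it: "The main outcome is defined as the time of cancer reoccurrence within 36 months after surgery", and censors patients who have no event by 36 months. Section 7 schedules chest CT up to 36 months.

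The Research time section sets the calendar: 400 patients in 2026, 600 in 2027, then "January 2028 to October 2028: Complete data collection for 400 patients", followed by "October 2028 to December 2028: Data organization and statistical analysis".

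**The concern.** The power of a time-to-event comparison depends on the number of events. Hazard ratio, alpha and power fix that number; turning it into patients needs the proportion who will have an event by the analysis. The protocol prints two medians and a 36-month window, which together imply that proportion, but 635 does not correspond to it. It corresponds to a much lower proportion that is not stated.

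If the medians and window are right, the trial enrols far more patients than 90% power requires. If the lower proportion is right for 36 months and the analysis follows the printed calendar, the trial falls well short of 90%. The text does not say which applies.

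The eligible population adds to the doubt about an 18-month control median. Inclusion criterion 2 admits anyone who will "Electively undergo minimally invasive (thoracoscopic or robotic) surgery for clinical stage I and II lung cancer", while the background says: "Stage I ground glass nodules, even if the pathological type is invasive adenocarcinoma and larger than 3cm, still have a 5-year 100% survival rate". That is a survival figure, not a recurrence figure, and the share of such patients is not given, so no loss of power is calculated from it.

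**Working it through.** **Inputs.** Medians 18 and 24 months, hazard ratio 0.75, power 90%, two-sided 0.05 and 635 per group (section 1.1); 1:1 allocation (Research Design); 36 months per patient (Main outcome measure; section 10); enrolment of 400/600/400 over months 0–12, 12–24 and 24–34 (Research time, reading its data collection as enrolment, which is an assumption). Constant hazards follow from section 1.1's own rule that the rate is proportional to 1/median.

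**1. Required events.**
- Schoenfeld: 4(1.960 + 1.282)² / (ln 0.75)² = 507.8, so 508.
- Freedman: (1.75/0.25)² × (1.960 + 1.282)² = 514.9, so 515.

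**2. Trying to reproduce 635 from the stated inputs.** Event proportions by 36 months:
- control: 1 − 2^(−36/18) = 0.750
- lidocaine: 1 − 2^(−36/24) = 0.646
- mean: 0.698

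Patients per group: 507.8/0.698/2 = 364 (Schoenfeld) or 514.9/0.698/2 = 369 (Freedman). Other variants at 36 months also miss 635: two-proportion formula 411 (430 with continuity correction); 10–20% loss 379 to 402; 1/median used directly as the hazard 309 to 314.

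**3. What 635 per group delivers on the stated inputs.** 1270 × 0.698 = 887 events; power = Φ(√(887/4) × 0.2877 − 1.960) = 0.990. The need at 90% is 2 × 364 = 728, so 1270 exceeds it by 542.

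**4. What 635 corresponds to.** 507.8/1270 = 0.400; in reverse, 507.8/0.40/2 = 634.8. Two routes give about 40%:
- *(a) 40% by 36 months.* Solving [p + 1 − (1 − p)^0.75]/2 = 0.40 gives a control proportion of 0.444, hence medians of about 42.5 and 56.7 months, not 18 and 24.
- *(b) The stated medians, analysed when accrual ends.* With uniform accrual over A = 34 months and analysis at month 34, the proportion is 1 − (1 − e^(−λA))/(λA) with λ = ln 2/median: 0.442 and 0.363, mean 0.403, giving about 630 (Schoenfeld) to 639 (Freedman) per group. With 400/600/400 accrual the mean is 0.392, giving 648 to 657. This abandons 36 months per patient: mean follow-up at the end of December 2028 (month 36) would be (400 × 30 + 600 × 18 + 400 × 7)/1400 = 18.3 months.

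**5. Power of 1270 evaluable patients at hazard ratio 0.75.**

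| Event assumption | Follow-up | Events | Power |
|---|---|---|---|
| Stated medians | 36 months each | 887 | 99% |
| Stated medians | Printed calendar, cut-off month 34 to 36 | 498–548 | 89–92% |
| 40% by 36 months | 36 months each | 508 | 90% |
| 40% by 36 months | Printed calendar, cut-off month 34 to 36 | 254–282 | 63–68% |

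**6. Sensitivity to the 36-month event proportion** (assumed values, not from the protocol; 36 months each): 70% gives 99% power; 40%, 90%; 35%, 86%; 30%, 80%; 25%, 73%; 20%, 63%.

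**The case against.** The strongest reply is that section 1.1 uses the medians only to obtain the hazard ratio and never says that 635 assumes 36 months of follow-up. On that view an input is missing, and no arithmetic error is shown. The hazard ratio of 0.75 is indeed correct, 635 × 1.10 = 698.5 rounds to 700, and no software error is proven. But the protocol prints medians, power, sample size and outcome window, and these cannot all hold together.

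Second, the stated medians do give about 635 on the protocol's own calendar (route b), with power of 89–92% under 400/600/400 accrual. This is true, and it may be how the figure arose. It works only by setting aside the 36-month window that defines the primary outcome.

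Third, the 18 months might be a median among patients who recur, which could coexist with about 40% recurrence: under route (a) the median time among control patients recurring by 36 months is 15.4 months. Section 1.1, however, uses 18 and 24 as group medians and derives the hazards from them.

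Fourth, the 63–68% combines an unstated event proportion with early analysis and uses 1270 patients, although censored patients also contribute. This stands as a caution: if all 1400 contributed fully, the same case gives 67–72%, still well below 90%. No combination that uses the protocol's own medians falls materially below 90%.

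Finally, section 10 models recurrence or death, while the medians are for recurrence. Counting deaths as further events would raise the 36-month proportion above 69.8% and, at the same hazard ratio, widen the gap from 635.

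**Conclusion.** The concern holds. With the stated medians, constant hazards and 36 months per patient, 90% power needs 364 to 369 per group, and 635 gives 99%. The 635 matches a 40% event proportion that the protocol does not state, and each of the two routes found to it contradicts a stated part of the protocol: the medians in one case, the 36-month window in the other. Which was used cannot be told from the text, nor can the direction of the error. The sample size of 1400 therefore has no consistent basis as written, and this must be fixed. The calendar results also assume that data collection in the Research time section means enrolment.

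**What to change.** In section 1.1, state the required number of events (508 by Schoenfeld), the overall 36-month event proportion expected for the eligible stage mix with its source, and the accrual and follow-up assumed. Reconcile these with the 18- and 24-month medians, the 36-month window and the Research time calendar, then restate the power that 1270 evaluable patients deliver. A short table of power against the 36-month event proportion, labelled as assumptions, would help but is optional.

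The fixed 36-month analysis can stay; neither an event-triggered analysis nor a change in eligibility is needed. Keeping it means correcting the calendar, because patients enrolled in October 2028 reach 36 months in October 2031, while the calendar ends analysis in December 2028. Otherwise the cost is a recalculation and protocol wording. The stated power may move in either direction, and no extra patients are requested.

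### The rationale separates stage I ground-glass nodules from the main target, but eligibility, minimisation, the Cox model and the planned event rate all ignore nodule type

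*Protocol*

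**What the plan says.** The cancer-staging paragraph of the Protocol's background states: "Stage I ground glass nodules, even if the pathological type is invasive adenocarcinoma and larger than 3cm, still have a 5-year 100% survival rate". It then describes stage I solid nodular disease and stage II disease and says of them: "These patients may benefit the most from lidocaine and will be the main target of this study". The next sentence announces breadth: "We will recruit patients with all cancer stages to understand potential differences in" response to lidocaine.

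Under Case selection, inclusion criterion 2 reads "Electively undergo minimally invasive (thoracoscopic or robotic) surgery for clinical stage I and II lung cancer". None of the 12 exclusion criteria mentions nodule type.

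The sample size section states "The median reoccurrence time described in the literature is 18 months", derives "Risk ratio=(1/24)/(1/18)=18/24=0.75" and specifies "90% efficacy, 0.05 significance level, bilateral significance level, HR 0.75". The result is 635 per group, raised to 700. No allowance for a low-event subgroup is described.

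Under Randomization: "The minimum criteria include age (<45 years, 45-65 years, 65-80 years), gender, trial center". The Statistics process section models time to recurrence or death. Its adjustment covariates include cancer staging but not nodule type.

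**The concern.** The Protocol itself treats nodule type as a strong prognostic divide within stage I, and then never uses it. Sites following the criteria may enrol patients whom the rationale places outside the main target and for whom it expects no deaths within the 36-month window. Adjusting for stage does not help, because the divide lies within stage I.

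There are two statistical consequences. Patients without events add nothing to the information on the hazard ratio. If they are also left in the same risk sets as higher-risk patients, the pooled hazard ratio is attenuated towards 1, because the lower-risk patients make up a growing part of those still at risk. Power for the intended HR of 0.75 in the target population then falls for both reasons, and the sample size section does not show that this was considered.

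**Working it through.** **Inputs from the Protocol.** HR 0.75; medians 18 and 24 months; two-sided 0.05; 90% power; 1:1 allocation; 635 per group (1,270), or 700 per group (1,400) after the increase; outcome window 36 months.

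**Assumptions, not in the Protocol.** A share g of patients in each arm has ground-glass nodules; these have no recurrence within 36 months; the HR is 0.75 in all others; hazards are constant.

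**The plan's own figure.** Required events (Schoenfeld) = 4 × (1.960 + 1.282)² / (ln 0.75)² = 508. With 36 months for every patient, the event probabilities are 1 − 2^(−36/18) = 0.750 and 1 − 2^(−36/24) = 0.646, mean 0.698. That needs 508 / 0.698 / 2 = 364 per group, not 635. The figure of 635 corresponds to an overall event fraction of 508 / 1,270 = 40%, which the Protocol does not state. The effect is therefore shown under both readings:

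- Reading A: 40% event fraction in the non-ground-glass patients (control hazard 0.0163 per month).
- Reading B: the stated medians, with a full 36 months for everyone.

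**Method.** Expected events D = N × (1 − g) × event fraction. The diluted HR solves the expected Cox score equation over 0 to 36 months with the two types mixed. Power = Φ(√D / 2 × |ln HR| − 1.96).

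| Share g | A, 635/group: events; HR; power | B, 635/group: events; HR; power | B, 700/group: power |
|---|---|---|---|
| 0% | 508; 0.75; 90% | 887; 0.75; 99% | 99% |
| 10% | 457; 0.76; 85% | 798; 0.77; 96% | 97% |
| 20% | 406; 0.76; 78% | 709; 0.79; 89% | 92% |
| 30% | 356; 0.77; 70% | 621; 0.80; 79% | 83% |

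Worked case, reading B, g = 30%, 635 per group: D = 1,270 × 0.70 × 0.698 = 621; diluted HR 0.801; √621 / 2 × 0.222 − 1.96 = 0.81; power 79%.

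**Cross-check.** A log-rank simulation (1,500 runs per setting) of reading B at 1,400 patients gave 96.7%, 90.6% and 82.7% at shares of 10%, 20% and 30%, close to the last column.

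**How much stratification recovers.** If the analysis is stratified by nodule type, a stratum without events contributes nothing and the HR in the other stays at 0.75. Reading B, g = 30%: √621 / 2 × 0.288 − 1.96 = 1.62, power 95% instead of 79%. Under reading A the same step gives 77% instead of 70%. Stratification removes the dilution but cannot replace the missing events.

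**The case against.** Four points can be made in the plan's defence.

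- **Breadth is declared.** A main target is not an only target, and the background says that patients of all stages will be recruited. This stands as far as intent goes: admitting ground-glass patients may be a choice and not an oversight. But that sentence concerns stage, conflicts with criterion 2, and does not make the sample size allow for low-risk patients.
- **The Protocol gives survival, not recurrence.** A reader might infer from the rationale that these patients will have almost no primary events. The text does not support that: a patient can recur and be alive at 5 years. Only the absence of deaths follows from the text.
- **The 18-month median may already describe the mix.** A reader might infer that it cannot hold in a population containing this group. That goes too far. The Protocol attributes it to similar populations, and an overall 18-month median is possible at any zero-event share below 50%; at 30%, 0.5 / 0.7 = 71% of the others would have to recur by 18 months. If the source had the same mix, some of the loss is built in.
- **Power below 90% at any share above zero** is true under reading A by construction, because that reading is calibrated to exactly 90% at zero. On the stated medians, power falls below 90% only from a share of about 20%. Reading B is itself generous, however: it needs 36 months per patient, while the Research time section has data collection running from January 2026 to October 2028, 34 months in all.

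Chance imbalance in nodule type between arms is a minor matter with 1,400 patients.

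**Conclusion.** The mismatch is plain in the text: nodule type matters in the rationale and appears nowhere in eligibility, minimisation, the Cox model or the event-rate assumption. The direction of the effect is the same under both readings. Its size is not fixed by the document, because it rests on an assumed ground-glass share and on assumed zero recurrence in that group. At shares of 10 to 30% with 635 per group, power would be 85 to 70% under the implied event fraction and 96 to 79% under the stated medians.

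It would be too strong to say that a null result could not be interpreted. The supported conclusion is that power in the intended population may be materially below the stated 90%, and that the Protocol does not show otherwise. This should be fixed before recruitment, but it does not invalidate the design.

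**What to change.** Reconcile the staging paragraph of the background with inclusion criterion 2, in one of two ways.

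1. **Align criterion 2 with the stated main target**, using a preoperative CT definition of nodule type that also says where part-solid lesions belong. A bare solid versus ground-glass rule would leave those unclassified. This narrows the population. The figure of about 8,000 lung operations per centre per year covers all lung surgery, so it does not by itself show that enough eligible patients remain.
2. **Keep ground-glass patients**, and (i) record nodule type from the preoperative CT and add it to the minimisation factors; (ii) stratify the primary Cox model and the log-rank test by it; (iii) base the planned event rate on the expected mix of nodule types and restate the power.

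Which population to study is the sponsor's choice. Under the second option the cost is protocol wording, one more minimisation factor and possibly a less favourable stated power. Nodule type is read from the preoperative CT, so no additional procedure is needed.
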